5.2. Institutional Review Board

5.3 Study Objectives

Primary Objective

- a. The primary objective is to evaluate the effects of inhaled nasal sodium pyruvate (N115) in patients with confirmed COVID-19 or flu infections by determining changes in the duration of an active infection by PCR from nasal.
 Secondary Objective
- **a.** The second objective is to evaluate the ability of the inhaled nasal sodium pyruvate therapy in subjects with COVID-19 or flu infections to improve symptoms by the use of a patient diary and by collecting periodic vital signs, especially body temperature, blood pressure and pulse/Ox.

5.4. Study Design Overview

Individuals that are symptomatic for COVID19/influenza will initially be tested by Dynamic DNA Labs or Trinity Healthcare (Screening Visit). If positive for COVID19/influenza, patient will then be solicited for participation in the trial within 24 hours. After signing Informed Consent, women of child-bearing age will provide a urine sample to test for pregnancy. They will be randomly assigned to either the placebo or drug groups in a double blinded fashion and be given a data logbook, or clinical app for their phone, in which they will record the number of coughs and other flu-like symptoms they experience each day. Patients will be contacted by phone and/or sent reminders through a clinical phone app every two days to review symptoms and protocol compliance and patients will be tested via nasal swab every other day. This will continue every other day until the subject tests negative for COVID-19/ influenza (which is

defined as a 2-Log reduction in virus titer or less than 1000 copies of viral RNA) or 14 days, whichever comes first. Personnel collecting swabs will wear N95 mask and face shield, disposable examination gloves and disposable gown while collecting nasal swabs from patients. Samples will be collected outdoors, weather permitting, or in a well ventilated room in inclement weather.

6.0. The criteria for patient selection and for exclusion of patients, and an estimate of the number of patients to be studied.

6.1. Subject Selection

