6.4 Inclusion of Women and Minorities

Every attempt will be made to include all genders, and minorities that present with an active COVID-19 or flu infection that are not exempted due to exclusion criteria.

7.0. A Description Of The Design Of The Study, Including The Kind Of Control Group To Be Used, If Any, And A Description Of Methods To Be Used To Minimize Bias On The Part Of Subjects, Investigators, And Analysts.

7.1. Assignment Of Subject Number And Randomization

This is a placebo controlled double blinded trial. Upon enrollment, each subject will be sequentially issued a unique subject number starting at 100. Once a number has been assigned to a subject, it cannot be re-assigned to another subject. Subjects will be encouraged to complete the study, although they may withdraw at any time without prejudice. Termination will be reported to the sponsor in a timely manner. Details of the reason(s) why a subject is dropped from the study will be documented. Enrollment will continue until the number of subjects specified in the protocol has been attained. The data from all subjects that have been given a study compound will be retained for analysis.

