7.3.1. Pre-study Visit

A pre-study visit will occur and the eligibility of the subject for inclusion determined. COVID19 or influenza positive patients will sign an Informed Consent (paper or eConsent), and a list of current medications will be taken. Urine samples from child-bearing aged women will be collected and analyzed for pregnancy (or last menstrual cycle recorded). During this visit, any flu-like symptoms will be noted, temperature, Pulse/Ox and blood pressure will also be measured. During this pre-study visit, the patients are to continue with their normal therapy, if any.

7.3.2. Study Visit 1

Only COVID19 or influenza single positive subjects meeting enrollment criteria will be enrolled after review of health information collected in the pre-study visit. The correct use of the N115 sodium pyruvate nasal spray will be demonstrated to COVID-19 or influenza infected subjects, and the subjects that have been confirmed to have an infection will administer their first dose while monitored in the clinic or via telehealth. (Nasal spray can be delivered to patient at time of telehealth visit by currier). The patients will be told to spray each nostril three times, three times per day: morning, mid-day, and evening. Patients will also be instructed on filling out the Daily Data Log form or in the use of the clinical symptoms app, which will be used to record administration of the drug doses, any flu-like symptoms, and any perceived adverse events.

7.3.3 Study Visit 2 etc.

At home or on-site follow-up visits will occur every two days after Study Visit 1. During this visit, a nasal swab will be taken to determine if the patient still has an active infection. Temperature, Pulse/Ox and blood pressure will also be examined during these visits. Study monitors will review the Daily Data Log form/ Clinical app and compliance with study protocol of N115 administration will be reviewed. If needed, additional bottles of N115 nasal spray will

be delivered to the patient in the clinic or via currier.

This process of testing every two days will continue until the particular subject proves to be virus free (2 Log or greater decrease in viral RNA or less than 1000 viral RNA copies) or 14 days, whichever is first. When the patient is virus free, he/she will be excused from the study. If the subject is virus free, they will be asked to provide a second nasal swab within 24 hours to verify the negative result.

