18.2. Data Collection, Management, and Statistical Analysis

The data management staff at the research clinic and lab (Trinity Healthcare and Dynamic DNA Labs) will collect and manage the data. Monitoring and auditing of the data will be

conducted by a staff member of Cellular Sciences remotely.

The basic statistical analysis will be repeated measurements of Analysis of Variance using baseline measurements as a covariant per subject. Group comparisons of N115 to placebo will be analyzed by ANOVA followed by Chi Square, Fisher Exact, and other appropriate significance tests. Data will be compared to placebo controls and current publicly available matched data and observed values compared. Time dependence in viral titer reduction will also be compared. [name] will be responsible for the statistical analysis. Analysis will be performed blinded.

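### Swabbing stops at each patient's own clearance, so the repeated-measures ANOVA in 18.2, if applied to viral load, would understate a real N115 effect

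*Combined protocol and SAP*

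**What the plan says.** Section 18.2 gives the main analysis: "The basic statistical analysis will be repeated measurements of Analysis of Variance using baseline measurements as a covariant per subject". It continues: "Group comparisons of N115 to placebo will be analyzed by ANOVA followed by Chi Square, Fisher Exact, and other appropriate significance tests", and adds: "Time dependence in viral titer reduction will also be compared". It names no response variable for the repeated-measures analysis, no method for the time comparison, and no rule for missing visits.

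Swabs are taken every other day. Section 7.3.3 says "This process of testing every two days will continue until the particular subject proves to be virus free", defined as "2 Log or greater decrease in viral RNA or less than 1000 viral RNA copies", or until 14 days have passed (5.4 says the same). Then: "When the patient is virus free, he/she will be excused from the study". One verification swab within 24 hours is requested after that.

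On retention, 7.1 says "The data from all subjects that have been given a study compound will be retained for analysis". The premature-withdrawal text in 9.0 and section 18.4 keep the data of patients who withdraw. None of these says how a cleared patient's later, untaken swabs are treated.

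The primary objective (5.3) is "determining changes in the duration of an active infection by PCR from nasal". How fast viral load falls is a further study question, in item 3 of the purpose section before 3.0.

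**The concern.** The variable being analysed decides when a patient stops contributing to it. Fast clearers leave first, so at each later visit the patients still swabbed are the slow ones. If N115 speeds clearance, this selection is stronger in the N115 arm, and the arms look more alike than they are.

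Textbook repeated-measures ANOVA needs every visit from every patient. Applied that way, it would analyse only those who had not met the stop rule before Day 14. Applied to whoever is left at each visit, it keeps more information but still compares selected groups. The two choices give very different answers, and the plan leaves the choice open until data are in hand. At stake is the size of the reported effect on viral load, in a trial with 15 patients per arm per virus.

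**Working it through.** **1. What the stop rule implies by itself.** A full series has 8 swabs (Days 0, 2, ..., 14) and requires that the rule is not met by Day 12. A 2-log fall over 12 days is 2/12 = 0.167 log10 per day. Apart from swab error, anyone falling at that rate or faster has no Day 14 swab. The 1000-copy limit (3 log10) stops patients with low baselines sooner still.

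**2. No plan figure to reproduce.** The documents give no titre mean, SD, rate of decline, effect size, alpha or power, only 15 per arm per virus (6.1.1). For scale, assuming two-sided 0.05 and 80% power, the detectable standardised difference is (1.96 + 0.84) × √(2/15) = 1.02.

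**3. Simulation, input set A (all assumed).** Baseline 6.5 log10 copies (SD 1.2). Daily decline placebo/N115 of 0.15/0.25, 0.20/0.35, 0.25/0.45 and 0.30/0.60. Slope SD 0.05–0.15, swab SD 0.4–0.5. The series stops at the first swab with a fall of at least 2 log10 or a value below 3 log10; the clearing swab is kept and the verification swab ignored. There were 300 replicates (40 for mixed models). Results at 15 per arm, as ranges over the four scenarios, for the baseline-adjusted average arm difference:

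| Handling | Share of full-data difference retained | Power |
|---|---|---|
| All swabs to Day 14 (no stopping) | 100% | 0.91–0.99 |
| Complete series only | −5% to 33% | 0.00–0.04 |
| All available swabs | 54–64% | 0.81–0.96 |
| Clearing value carried forward | 44–68% | 0.77–0.89 |
| Mixed model, random intercept only | 64–76% | 0.85–0.97 |

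A complete series remains in 0.02–1.1 of 15 N115 patients and 2.5–7.1 of 15 placebo patients.

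Arm difference by visit (30 per arm, three scenarios), patients still swabbed against full data:

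| Decline | Day 4 | Day 8 | Day 12 |
|---|---|---|---|
| 0.20/0.35 | −0.62 vs −0.64 | −0.88 vs −1.23 | −0.79 vs −1.68 |
| 0.25/0.45 | −0.80 vs −0.84 | −1.02 vs −1.57 | −0.87 vs −1.82 |
| 0.30/0.60 | −1.15 vs −1.24 | −1.21 vs −2.07 | −1.02 vs −1.89 |

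The loss, 1 − observed/full, is 3–7% at Day 4 (for example 1 − 0.62/0.64 = 3%), 28–42% at Day 8 (1 − 0.88/1.23 = 28%; 1 − 1.21/2.07 = 42%) and 46–53% at Day 12.

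**4. Simulation, input set B (also assumed).** Baseline 6–7 log10 (SD 1), slope SD 0.15, swab SD 0.5, decline 0.25/0.35 and 0.35/0.50.
- Complete series: about 3.6–4.0 placebo and 1.5 N115 patients of 15 in the first case, about 1.5 and 0.2 in the second. The slope difference is about −0.03 against a true −0.10 to −0.15, so 1 − 0.03/0.10 = 70% to 1 − 0.03/0.15 = 80% is lost.
- Available swabs at Day 8: −0.42 to −0.60 against −0.79 to −1.20, a loss of 1 − 0.42/0.79 = 47% to 1 − 0.60/1.20 = 50%.
- Average over all available swabs: −0.35 to −0.50 against −0.80 to −1.25, a loss of 56–60%.
- Equal decline in both arms (0.35/0.35): every method gives about zero.

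**5. Does a random-slope likelihood model repair it?** Stopping depends only on swabs that were observed, so a correctly specified likelihood remains valid.
- Set A, 30 per arm: −0.155, −0.205 and −0.309 for true −0.15, −0.20 and −0.30.
- Set A, 15 per arm: −0.123, −0.170, −0.224 and −0.329 for true −0.10, −0.15, −0.20 and −0.30, somewhat too large (40 replicates each).
- Set B, 15 per arm: means −0.100 and −0.150, on target. Power was 0.28 and 0.52, against 0.30 and 0.50–0.53 for all available swabs and 0.36–0.38 and 0.71–0.72 without stopping. Of 60 fits per scenario, 8–16 failed to converge or gave no usable standard error.
- When titre was made to level off after clearance, the model gave −0.154 against −0.065: extrapolation past clearance overstates the difference.

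**The case against.** **The plan does not say that titre is analysed by this ANOVA.** That is so: 18.2 names no response variable, the time comparison of titre has its own sentence, and coughs, symptoms and vital signs are repeated measures too. But no other longitudinal method is named, so a statistician following 18.2 would have nothing else to use for titre.

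**The largest losses need deletion of incomplete series.** A reader might infer that most of the N115 effect will be lost. The documents do not support that. They state no complete-case rule, and the retention wording in 7.1, 9.0 and 18.4 points away from one. That wording governs which patients stay in the data set, though, not how missing visits are modelled. With all swabs used, a third to a half or more of the average difference still goes, and part of that is only heavier weight on early visits.

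**The remedy may not raise power.** This stands. In set B at 15 per arm, the random-slope model removed the bias with no visible gain over all available swabs.

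**The remedy was tested mainly where it should succeed.** This also stands. The curves were linear with normal random slopes, and the levelling-off run shows what happens otherwise.

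**Day 4 could simply be named as the comparison.** Few patients have stopped by then, but in set B its power at 15 per arm was only 0.20–0.21 and 0.36–0.38. It is an option, not a requirement.

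**Conclusion.** The concern holds as a mismatch between the stop rule and the only longitudinal method named. If N115 speeds viral decline, a complete-series ANOVA would lose most of the effect. An analysis of all available swabs would understate the average difference by about 36–46% in set A and 56–60% in set B. The shortfall is slight at Day 4 and substantial from Day 8. The direction follows from the design; the sizes rest on assumed titre curves and cannot be fixed from the documents.

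Two further inferences should be resisted. The stop rule does not create false positives here: with equal decline in both arms, no method showed a difference. Nor does this point undermine the primary objective, since duration of infection is a separate question with its own analysis needs. For that reason the point should be fixed but is not critical to the trial.

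**What to change.** In 18.2, name the viral-load analysis separately:
- a likelihood-based linear mixed model on log10 copies, with Day 0 in the model, fixed effects for arm, day and arm-by-day, and a random intercept and slope per patient;
- every swab taken is used, no patient is dropped for an incomplete series, and no value is carried forward after clearance;
- the result is the arm difference in rate of decline over the swabbed period, with a confidence interval, not extrapolated past clearance.

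The random slope matters, because a random intercept alone kept only 59–76% of the average difference (set A, 15 and 30 per arm). Since fits may fail at 15 per arm, state a fallback in advance: for example, uncorrelated intercept and slope, then a random intercept alone, reported as likely to understate the effect. State too that roughly linear log10 decline is assumed, and check it on the observed swabs.

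The cost is wording only: no extra swabs, visits or patients. The price is reliance on linearity and some risk of non-convergence.

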18.3. Study Monitoring

A Study Monitor who will be responsible for auditing data will be appointed by Cellular Sciences. The Monitor will visit the clinical site two or three times during the trial to assure that all data are being collected and that the Case Report Forms are completed and correctly filled out. Alternatively, virtual visits may be conducted due to COVID19 exposure concerns.

18.4. Data from Patients Who Withdraw from the Study

If a subject withdraws from a study, the data collected on the subject to the point of withdrawal will remain part of the study database and will not be removed.

The investigator may ask a subject who is withdrawing whether the subject wishes to provide continued follow-up and further data collection subsequent to their withdrawal from the interventional portion of the study. Under this circumstance, the discussion with the subject would distinguish between study-related interventions and continued follow-up of associated clinical outcome information, such as medical course or laboratory results obtained through non-invasive chart review and address the maintenance of privacy and confidentiality of the subject's information.

If a subject withdraws from the interventional portion of the study but agrees to continued follow-up of associated clinical outcome information as described in the previous bullet, the investigator must obtain the subject's informed consent for this limited participation in the study (assuming such a situation was not described in the original informed consent form). In accordance with FDA regulations, IRB approval of informed consent documents would be required (21 CFR 50.25, 56.109(b), 312.60, 312.66, 812.100).

If a subject withdraws from the interventional portion of a study and does not consent to continued follow-up of associated clinical outcome information, the investigator must not access for purposes related to the study the subject's medical record or other confidential records requiring the subject's consent. However, an investigator may review study data related to the subject collected prior to the subject's withdrawal from the study, and may consult public records, such as those establishing survival status.

18.5. Product Packaging

The product packaging has complied with FDA regulations. The nasal spray will be contained in a sterile plastic vial that can be squeezed to administer the correct dosage. The packaging meets 21CFR312.6 including the statement "New Drug - investigational use only." The vials necessary for each study period (i.e. ~14 days) will be placed in a plastic bag with the patient's number.

18.6. Product Storage Requirements

 $18.6.1 \ At \ Research \ Center$ The products are to be stored at room temperature, but not above $85^{o}F$

18.6.2 In Home

The products are to be stored at room temperature, but not above 85°F

18.7. Record Retention

All records will be kept by the clinic for a period of three years. After that, they will be sent to Cellular Sciences.

18.8. Additional Studies

No additional studies are planned at this time.

19.0 Reports on Adverse Events

19.1 Definition of an Adverse Event

CTCAE term (Adverse event description) and grade: The descriptions and grading scales found in the revised NCI Common Terminology Criteria for Adverse Events (CTCAE) version 3.0 will be utilized for adverse event reporting. All appropriate treatment areas should have access to a copy of the CTCAE version 3.0. A copy of the CTCAE version 3.0 can be downloaded from the CTEP web site (http://ctep.cancer.gov/reporting/ctc.html).

"Expectedness": Adverse events can be "Expected" or unexpected. Attribution of the adverse event (Section 4.8.5):

Definite – The adverse event is clearly related to the study treatment.

Probable – The adverse event *is likely related* to the study treatment.

Possible – The adverse event may be related to the study treatment.

Unlikely – The adverse event *is doubtfully related* to the study treatment.

Unrelated – The adverse event *is clearly NOT related* to the study treatment.

A serious adverse event (SAE) is defined as *any expected or unexpected adverse event* (AE, generally equivalent to CTCAE ver 3.0 grades 3, 4 or 5) that is *related or unrelated* to the intervention that results in any of the following outcomes:

- Death
- A life-threatening event
- In-patient hospitalization (not required as part of the treatment) or prolongation of existing hospitalization
- A persistent or significant disability/incapacity
- A congenital anomaly/birth defect
- Causes cancer
- Is an overdose

Certain medical events that may not result in death, be life-threatening, or require hospitalization, may also be considered a serious adverse event when appropriate medical or surgical intervention is necessary to prevent one of the outcomes listed above.

Unexpected Adverse Event - Any event in which the severity or specificity is not consistent with the risk information described in the protocol, and the event is not anticipated from the subject's disease history or status.

Expected Adverse Event - Any event in which the severity or specificity is consistent with

the risk information described in the protocol or is anticipated based on the subject's medical history.

Important medical events that may not be immediately life-threatening or that do not result in death or hospitalization may be considered SAEs when, on the basis of appropriate medical judgment, they may jeopardize the patient and may require medical or surgical intervention to prevent one of the outcomes listed above.

All deaths, regardless of cause, must be reported for patients on study and for deaths occurring within 30 days of last study drug dose.

19.2. Examples of Adverse Events

- Inter-current illnesses
- Injuries
- New symptomatology (this does not include symptoms expected as a result of the subject's condition unless it is beyond what is normally expected)
- Significant laboratory abnormalities
- New abnormal physical exam findings
- Significant exacerbation of pre-existing conditions

19.3. Recording and Documentation of Adverse Events

Any adverse event (i.e., a new adverse event or an exacerbation of a pre-existing condition) with an onset date after study drug administration should be recorded as an adverse event on the Case Report Form (CRF). All adverse events must be recorded on the appropriate CRF regardless of the severity or relationship to study medication.

An adverse event or laboratory abnormality with an onset date before study drug administration is considered to be pre-existing in nature. These pre-existing events, will be noted in the CRFs.

All SAEs occurring during this study, whether observed by the physician, nurse, or reported by the patient, will be recorded on the Florida Advanced Medical Research Adverse Events form

19.5 IRB Notification

The Investigator is responsible for promptly notifying the Institutional Review Board of all serious adverse events and providing appropriate documentation. The Investigator should notify the IRB as soon as is practical. Notification should be in writing where this is required by local regulatory authorities and in accordance with the local institutional policy.

Adverse events must be reported to the Investigator and IRB according to definitions and guidelines at http://www.infosci.coh.org/ocrqa/forms/guidance.doc and which are defined herein. AEs will be monitored by the PMT. Less than serious adverse events will be reported only at the time of protocol continuation reports.

Cellular Sciences may request additional information from the Investigator to ensure the timely completion of accurate safety reports.

19.6 Attribution

For reporting purposes, attribution is the assessment of the likelihood that an AE is caused by the research agent or protocol intervention. The attribution is assigned by the treating physician/Principal Investigator after considering the clinical information, the medical history of the subject, and past experience with the research agent/intervention. This is recorded using the Adverse Event Report (COH AER) form (http://resadmin.coh.org/doc /irb3820.doc) in one of five categories scored as the following: 5=related, 4=probably related, 3=possibly related, 2=unlikely related, and 1=unrelated.

